4.3 Duration of Follow Up

The study will collect data at 3 points: baseline before entry into therapy session, midway through the therapy session after 9 visits and after 18 visits. There is to be no follow up after the post 18th session testing.

4.4 Removal of Patients from Protocol Therapy

Patients may be removed from therapy if there is a change in medical status. The Principal Investigator may also decide if the patient is unable to continue for any extenuating circumstances to remove the subject from the study, and document the reason for study removal and the date the patient was removed in the Case Report Form.

5.0 STUDY PROCEDURES

5.1 Screening/Baseline Procedures

Subjects will be randomized into 2 separate groups, either SMA or IPT. We will enroll 80 subjects, 40 in each group, planning for a 30% attrition rate. These subjects will be recruited when they are referred to RIC's stroke rehabilitation outpatient clinics at RIC's flagship at [name], or RIC Northshore in Northbrook IL or RIC Willowbrook in Willowbrook, IL. We will also recruit from local physicians or RIC's Clinical Neuroscience Research Registry for subjects who are potential candidates for outpatient physical therapy. They will be directed to a physical therapist who will inform them of the time commitment required and questioned regarding the inclusion/exclusion criteria. Once subjects have agreed to participate in the study, they will come to RIC and be consented at one of the clinics at the Rehabilitation Institute of Chicago. Study staff will explain the study, a written consent form will be signed by the subject and witnessed by study researchers, a copy will be given to the subject and a copy will be kept in the subject's folder in a secure, locked cabinet in the lab's locked office.

After consenting, subjects will undergo a physical evaluation and screening exam by a licensed PT. If they meet study criteria, they will be randomly placed into either the SMA group or the IPT group using a random number generator and they will be entered into the study. Once they are enrolled, baseline outcome measures will be assessed by a blinded research PT.

In addition, subjects will have a baseline measure of their cortical excitability through TMS. This will be conducted at University of Illinois, Department of Physical Therapy. TMS sessions will last approximately 2 hours.

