4.0 TREATMENT PLAN

4.1 Treatment Sessions

Once subjects have been consented and they meet study inclusion and exclusion criteria, they will be randomly placed into either the SMA group or impairment based (IPT) group. The Physical therapy treatment sessions will follow the guidelines below:

- IPT group
 - Assessment (strength, flexibility, balance, sensation, endurance, transfers, gait). Treatment will be divided into: 15 min balance training, 15 minutes functional mobility (transfers, strength or flexibility training) and 15 min high intensity gait training

- SMA group
 - Assessment (strength, flexibility, balance, sensation, endurance, transfers, gait)
 - Treatment consists of 30minutes high intensity gait training with device, 15 minutes functional mobility with device (eg stairs, ramps, curbs, uneven surfaces, indoors, outdoors)

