5.2 Procedures during Treatment

After the baseline testing is completed, subjects will begin 18 sessions of PT training in the outpatient clinic with a licensed RIC clinical PT. These sessions will last from 45 to 60 minutes. Their sessions will be recorded in RIC's electronic documentation system Cerner.

A blinded research physical therapist will test the outcome measure at baseline, Mid Testing after Session 9, at Post Testing after Session 18 and at 3 month follow up testing after Session 18.

IPT group	Baseline TMS	Baseline testing (blinded PT)	Sessions 1-9 3 x wk	Mid Testing (blinded PT)	Sessions 10-18 3 x wk	Post testing TMS	Post testing (blinded PT)	Follow up testing (blinded PT) 3 months post
SMA group	Baseline TMS	Baseline testing (blinded PT)	Sessions 1-9 3 x wk	Mid Testing (blinded PT)	Sessions 10-18 3 x wk	Post testing TMS	Post testing (blinded PT)	Follow up testing (blinded PT) 3 months post

The TMS protocol

We will test descending corticospinal drive to the rectus femoris, vastus lateralis, lateral hamstrings, tibialis anterior, and medial gastrocnemius muscles. These muscles have the biggest representation in the motor cortex and are most involved during the gait cycle.

Maximum Voluntary Isometric Contractions (MVIC): Before beginning the TMS protocol, an estimate of MVIC will be obtained for each muscle with the subject positioned in sitting on a chair, with the knee joint at 90 degrees of flexion and ankle in neutral position. Manual resistance will be provided by one of the investigators as the subject tries to extend or flex the knee, dorsiflex or plantarflex the ankle. Subjects will then be seated with the feet constrained by flexible 4.0 kg weights placed over the dorsum of each foot. The subject will be given real time feedback of muscle activity to match a target contraction corresponding to 10% MVIC for individual muscles during TMS measurements (details below).

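### Random placement comes before the baseline outcome measures, and nothing withholds the arm until baseline is complete, so effort-dependent and self-reported baseline values carry an avoidable (undemonstrated) risk of an arm-related shift

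*Combined protocol and SAP*

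**What the plan says.** Section 5.1 gives the sequence. After consent, a licensed therapist does an evaluation and screening exam; then "If they meet study criteria, they will be randomly placed into either the SMA group or the IPT group using a random number generator". The next step is: "Once they are enrolled, baseline outcome measures will be assessed by a blinded research PT". The following paragraph adds TMS: "In addition, subjects will have a baseline measure of their cortical excitability through TMS".

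Section 4.1 has the same trigger, with consent and eligibility as the only conditions: "Once subjects have been consented and they meet study inclusion and exclusion criteria, they will be randomly placed into either the SMA group".

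Other places bear on timing without changing that order:

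- Section 4.3 fixes baseline relative to treatment, not to allocation: "baseline before entry into therapy session". Section 5.2 does the same: "After the baseline testing is completed, subjects will begin 18 sessions of PT training in the outpatient clinic".
- The flow table in 5.2 shows baseline TMS and baseline testing inside rows already labelled IPT and SMA.
- The table in 5.3 puts consent and baseline in one column and has no row for randomisation.
- Section 8.2 speaks of assigning subjects who are already enrolled, whereas 5.1 uses enrolment for a step that follows random placement.

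On blinding, the documents cover one role, the outcome tester: "A blinded research physical therapist will test the outcome measure at baseline, Mid Testing after Session 9". They state no blinding for whoever performs TMS, and they do not say when participants or treating staff are told the arm.

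**The concern.** A baseline value should be free of any influence of the allocation. If a participant already knows the arm when baseline is taken, enthusiasm or disappointment can alter how hard they walk or how they rate themselves. A blinded tester does not close that route, because the influence runs through the participant.

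Several baseline measures are sensitive to this. The 10-metre walk (the primary outcome in 2.1) is walked at self-selected and maximum safe speed. The 6-minute walk and the five-times sit-to-stand also depend on effort. Items 8 to 14 in 5.2 are seven self-report scales.

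Section 8.3 compares outcomes within subjects and between groups by multiple ANOVAs and does not say how baseline enters. A shift in one arm's baseline would pass in full into a change-score or group-by-time comparison, in part into a baseline-adjusted one, and not at all into a comparison of post values alone.

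**Working it through.** **1. Order of events.** Reading 4.1 and 5.1 together gives: consent, screening exam, random placement, entry into the study, baseline outcome measures, sessions. Sections 4.3, 5.2 and 5.3 do not contradict this. Section 8.2 uses the word enrolled differently, and read alone could allow baseline before assignment. It does not describe baseline testing, however, so the explicit sentence order in 5.1 governs. For TMS the order is inferred only from its place in the text and from the arm-labelled rows of the flow table.

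**2. What is known before allocation.** Section 3.1 requires an initial gait speed above 0.4 and below 0.8 m/s. The 10-metre walk entry in 5.2 repeats speed as an exclusion. Since criteria must be met before random placement, a gait speed must exist by then. No section names it as the analysed baseline or says under which walking condition it is taken. It does not cover the other outcomes.

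**3. Size, as an illustration.** There is no stated figure to reproduce, since the documents give no SD, effect size or shift.

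Inputs from the documents:

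- 40 per arm with 30% attrition ("We will enroll 80 subjects, 40 in each group, planning for a 30% attrition rate"), so 40 × 0.70 = 28 per arm.
- A 90% confidence level (8.3), taken as two-sided alpha 0.10; sidedness is not stated.
- A small meaningful change of 0.06 m/s (5.2).

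Assumptions:

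- A shift d = 0.02 m/s in one arm, which is 0.02/0.06 = 33% of the small change.
- An SD of 0.10, 0.15 or 0.20 m/s, for the change score or for the residual after adjustment.
- A baseline slope b of 0.5 to 0.9 for the adjusted analysis.
- No true treatment effect.

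Bias = b × d, with b = 1 for change scores. Noncentrality = bias / (SD × √(2/n)). The rejection rate comes from the noncentral t distribution. For example, with n = 28 and SD 0.10, the standard error is 0.10 × √(2/28) = 0.0267, the noncentrality is 0.02/0.0267 = 0.75, and the rate on 54 df is 0.191.

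| Analysis | Bias (m/s) | SD 0.10 | SD 0.15 | SD 0.20 |
|---|---|---|---|---|
| Change score, 28 per arm (54 df) | 0.020 | 0.191 | 0.141 | 0.123 |
| Change score, 40 per arm (78 df) | 0.020 | 0.230 | 0.159 | 0.133 |
| Adjusted, b = 0.5, 28 per arm (53 df) | 0.010 | 0.123 | 0.110 | 0.106 |
| Adjusted, b = 0.9, 28 per arm (53 df) | 0.018 | 0.174 | 0.133 | 0.119 |
| Post values only | 0 | 0.10 | 0.10 | 0.10 |

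**4. The same question without choosing d.** The shift that would take the change-score rate from 10% to 15% at 28 per arm is 0.0148, 0.0221 or 0.0295 m/s for the three SDs. Divided by 0.06, that is 25%, 37% or 49% of the small meaningful change.

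**5. After the change.** If the arm is unknown to the participant when baseline is taken, the expected shift from this source is zero and the rate stays at 10% under every row of the table.

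**The case against.** The strongest reply is that the harm needs three things together: disclosure before baseline, a response that differs by arm, and an analysis that uses baseline. The documents show neither of the first two. On the third, 8.3 can be read as between-group ANOVAs at each visit, which would carry no baseline shift into the later visits. All of this stands. A reader might infer from the sequence that participants are told their arm before baseline, or that the primary result will be biased. The documents support neither inference; they only fail to prevent the first.

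A second reply is that gait speed is known before randomisation because eligibility depends on it. This also stands, and it weakens the point for the primary outcome. It does not dispose of it, because the plan never says that the screening speed is the baseline to be analysed. Naming it as such would be a simple repair for gait speed alone, provided it is the same test in the same walking condition. The other effort-dependent tests and the self-report scales would remain exposed.

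A third reply is that participants will know their arm at the mid, post and follow-up tests in any case, since one arm wears a device. That is true, and reordering does nothing there. It is no reason to leave baseline open as well.

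Finally, the rates in the table could be mistaken for estimates for this trial. They are not: every figure above 10% follows from an assumed shift, SD and, where used, slope.

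**Conclusion.** The point holds as a sequencing weakness. Sections 4.1 and 5.1 place random allocation before the baseline outcome measures, and no section keeps the arm from participants until those measures are done. That reading is firm for the clinical and self-report measures and only inferred for TMS. The mixed use of enrolled in 5.1 and 8.2 should be reconciled, but it does not reverse the order.

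The resulting risk is avoidable but undemonstrated, and its size cannot be derived from the documents. It applies mainly to the effort-dependent tests other than gait speed and to the seven self-report scales. It is smaller for gait speed because of the eligibility measurement. The illustrative 12-19% (13-23% with 40 per arm) shows only that a shift well below the plan's own small meaningful change could matter for a change-score analysis, if such a shift occurred. This is a low-cost improvement worth making, not a flaw that invalidates the design.

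**What to change.** **Sections 4.1 and 5.1.** Reorder to consent, eligibility screen, all applicable baseline measures, then allocation. Suggested wording: *The allocation is generated, or is disclosed to the participant and treating staff, only after the last applicable baseline measure is complete; TMS counts only where the participant is compatible with it and tolerates it.* The TMS clause is needed because 3.1 makes TMS conditional on compatibility and 6.1.5 allows testing to be terminated. Use enrolled in one sense in 5.1 and 8.2.

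**Section 5.3.** Separate consent from baseline as needed and add a randomisation row placed after baseline.

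**Section 8.3, as a separate change at no cost in data.** Adjust the between-group comparison of gait speed for a baseline gait speed obtained before disclosure, in the same walking condition (self-selected or maximum) as the outcome.

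**Cost.** The change is protocol wording and one table row, with no added tests or visits and no change to the sample size. There are three downsides:

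- If allocation is delayed, some people may complete baseline, including about 2 hours of TMS, and never be randomised.
- If only disclosure is delayed, people who leave before baseline is finished still count as randomised.
- Device fitting and therapist scheduling may have to wait for baseline TMS, which is done at another institution. The documents do not establish that this adds no delay.

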Title	Randomized Control Trial Comparing Walking Task Specific Training with Stride Management Assist (SMA) Device vs. Functional Task Specific training on Functional Walking Ability in Outpatient Stroke Rehabilitation.
Short Title	Impairment vs. Functional Walking Training in Sub-Acute and Chronic Stroke (match this to title used it ClinicalTrials.gov)
Protocol Number	STU00085161
Methodology	Randomized Controlled Trial with 2 arms
Study Duration	1 year
Study Center(s)	Single site, multiple clinics within RIC's flagship hospital and it's outpatient clinics
Objectives	Determine if Honda Stride Management Assist vs. traditional Functional Gait Therapy increases Gait speed and function post stroke
Number of Subjects	80
Diagnosis and Main Inclusion Criteria	Cerebrovascular accident (CVA), post 30 days, Gait speed between 0.4 m/s and 0.8 m/s, MMSE > 17, unsupported sitting >30 s, walk at least 10m with up to max assist, follow instructions, physician clearance for participation
Study Product(s), Dose, Route, Regimen	Honda Stride Management Assist device in outpatient physical therapy
Duration of administration	18 Sessions of Outpatient Physical Therapy + 4 Sessions of testing
Reference therapy	Traditional Functional Mobility Training Physical Therapy
Statistical Methodology	Multiple ANOVAs

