1.3 Rationale

There is substantial evidence that post stroke recovery can last for greater than a year³. Due to cost pressures, various forms of therapies have been assessed for their effectiveness and efficiency. Task specific training post stroke has been found to be a very effective strategy for gait retraining^{10,11}. Impairment based physical therapy is another methodology practiced in clinical settings where the training is based on progressive strength and balance exercise program in the outpatient setting¹². The SMA group (task specific training) will be trained to simulate the demands of overground walking. The impairment based group will match the SMA group in intensity but will be focused on balance and other functional goals rather than explicitly on walking. The rationale of this study is to assess task specific training with SMA vs. impairment based training. To this end, we will use the Stride Management Assist device by Honda Corporation and compare it to impairment based physical therapy in outpatient sessions.

The enhancement of corticospinal excitability may help account for the long-term plasticity and improved motor control in people with stroke. To study this, we will measure corticospinal excitability of the lower limb muscles using Transcranial Magnetic Stimulation TMS. TMS is a safe and non-invasive method that has been widely used to study cognition, brain-behavior relations and the pathophysiology of various neurologic and psychiatric disorders.

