3.1 Inclusion Criteria

- \geq 30-days post stroke
- Age: 18-85 Years
- Initial gait speed of > 0.4 m/s and < 0.8 m/s
- Adequate cognitive function (MMSE score > 17)
- Subject is willing to be randomized to the control group or the treatment group.
- Ability to sit unsupported for 30 seconds
- Ability to walk at least 10m with maximum 1 person assist,
- Ability to follow a three-step command
- Physician approval for patient participation
- Living in the community post-stroke with ability to travel to the intervention site to participate in the outpatient program and able to perform the HEP program in the residential facility.
- Willing to carry wireless body sensors through the period of the study and to follow-up time period, post inpatient stroke, cardiac, pulmonary, or any other lower extremity physical rehabilitation

- \geq 90 days post major orthopedic surgery (i.e. hip, knee, and/or ankle joint replacement)
- \geq 6 months post CABG or cardiac valve procedure
- Able and willing to give written consent and comply with study procedures, including follow-up visits
- Willing to participate in two Transcranial Magnetic Stimulation sessions if they meet compatibility requirement.
- Cannot not be participating in any other structured outpatient or home health physical therapy program

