8.2 Sample Size and Accrual

A total enrollment of 80 subjects is estimated for this study. Each enrolled subject is randomly assigned to either one of the groups (SMA or IPT; 40 participants per group). A detailed description of study procedures and study endpoints are provided in section of 5.0

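### The allocation scheme is named only as a random number generator and the analysis names no covariate, so nothing secures 40 per group or controls time since stroke

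*Combined protocol and SAP*

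**What the plan says.** Section 5.1 gives the only description of allocation: subjects who meet the criteria "they will be randomly placed into either the SMA group or the IPT group using a random number generator". The same section sets the size: "We will enroll 80 subjects, 40 in each group, planning for a 30% attrition rate". Section 8.2 repeats it ("SMA or IPT; 40 participants per group"). Blocks, strata, minimisation, the list holder and concealment are not described anywhere.

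On the population, section 3.1 sets a lower limit ("30-days post stroke") and no upper one, and the short title in the synopsis is "Impairment vs. Functional Walking Training in Sub-Acute and Chronic Stroke". Section 1.3 notes that "post stroke recovery can last for greater than a year". The synopsis describes the setting as "Single site, multiple clinics within RIC's flagship hospital and it's outpatient clinics", and section 5.1 names three clinics.

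Section 8.3 plans multiple ANOVAs within and between subjects at a 90% confidence level. It lists no model terms and mentions neither time since stroke nor clinic.

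**The concern.** Two things are left to chance. The first is the arm sizes: the plan states 40 per group but describes nothing that would produce it. The second, which matters more, is time since stroke. Subjects one month after a stroke and subjects years after one may recover at different rates whatever the treatment. If one arm draws more sub-acute subjects, part of its gain in gait speed may be spontaneous recovery, and no stated model term would separate the two. Even with balanced arms, variation due to phase stays in the residual and widens the interval for the treatment contrast. Both time since stroke and clinic are known at entry, so both can be handled cheaply in advance. An adjustment chosen after the data are seen is less credible.

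**Working it through.** **Inputs from the documents:** N = 80, 40 per group, 30% attrition (5.1, 8.2); small meaningful change in gait speed 0.06 m/s (5.2, 10 Meter Walk Test).

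**Assumptions, not in the documents:** simple 1:1 allocation; sub-acute share one half (range 20-50%); extra gain in sub-acute subjects 0.10 m/s (range 0.05-0.15); SD of change within phase 0.15-0.20 m/s.

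**The plan's own figure.** 80 × 0.70 = 56 completers, 28 per arm. The figure of 80 itself cannot be re-derived, because no effect, SD or power is given.

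**Arm sizes under simple allocation.**
- P(exactly 40/40) = C(80,40)/2^80 = 0.089.
- P(45/35 or worse) = 2 × P(Bin(80, 0.5) ≤ 35) = 0.314.
- P(50/30 or worse) = 0.033.

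**What unequal arms cost.** Efficiency relative to 40/40 is 4·n1·n2/80².
- 45/35: 4 × 45 × 35/6400 = 0.984.
- 50/30: 4 × 50 × 30/6400 = 0.938.

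**Imbalance in phase.** With s sub-acute and n − s chronic subjects, the SMA counts are a ~ Bin(s, 0.5) and b ~ Bin(n − s, 0.5). The gap in sub-acute share is |a/(a+b) − (s−a)/(n−a−b)|. Summing the exact probabilities of a gap of 15 points or more:
- Exactly half sub-acute: 21.9% at n = 80 and 23.6% at n = 56.
- Sub-acute count itself random around one half: 18.7% at n = 80 and 25.4% at n = 56.
- At n = 80 with a lower sub-acute share: about 15% at a share of 30%, and 10-11% at 20%.

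**Effect on the contrast.** A 15-point gap shifts the treatment difference by 0.15 × 0.10 = 0.015 m/s, a quarter of 0.06. With a gain of 0.05 or 0.15 m/s the shift is 0.0075 or 0.0225 m/s. The standard error at 28 per arm is SD × √(2/28) = 0.040 m/s (SD 0.15) to 0.053 m/s (SD 0.20). The 0.015 m/s shift is therefore 0.015/0.053 = 0.28 to 0.015/0.040 = 0.37 of a standard error.

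**Precision from adjusting for phase.** The share of variance due to phase is p(1−p)g²/(SD² + p(1−p)g²). With p = 0.5 and g = 0.10, p(1−p)g² = 0.0025.
- SD 0.15: 0.0025/(0.0225 + 0.0025) = 10%.
- SD 0.20: 0.0025/(0.0400 + 0.0025) = 5.9%.
- The standard error falls by 1 − √0.90 = 5% and 1 − √0.941 = 3%.

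**Permuted blocks stratified by phase only.** An unfinished block of 4 can put each stratum at most 1 off an even split, so two strata give 42/38 at worst. A block of 6 can be 1.5 off, giving 43/37 at worst. In simulation, exactly 40/40 occurred in about 62% of trials with blocks of 4 and about 56% with mixed blocks of 4 and 6. A phase gap of 10 points or more did not occur. Crossing phase with three clinics (six strata, blocks of 4) gives exactly 40/40 in only 36-37% of trials, with a worst case of 46/34.

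**The case against.** A reader might infer that the trial uses plain coin-toss allocation. The documents do not say so. A random number generator can also produce a blocked or stratified list, and a stated 40 per group fits a restricted list at least as well. The documented defect is an unspecified scheme, and the 8.9% and 31% figures depend on the simple reading. It remains true that simple allocation would comply with the text as written.

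A reader might also infer bias, or a material loss of power from unequal arms. Neither follows. Simple randomisation is unbiased, the standard error already allows for chance imbalance, and 45/35 keeps 98.4% of efficiency.

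Nor does section 1.3 establish that recovery differs strongly by time since stroke. It says only that recovery can continue late, so the size of the phase effect has to be assumed. Eligibility also narrows the population (gait speed between 0.4 and 0.8 m/s, living in the community).

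Finally, covariate adjustment alone would recover most of the precision without touching the allocation list. That is fair: the model terms carry most of the benefit, and stratification adds protection against chance imbalance at little extra cost.

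**Conclusion.** The point holds as an inexpensive improvement to an under-specified plan. It does not show that the comparison is invalid. Neither the 40 per group nor balance on time since stroke is secured by anything written, in allocation or in analysis. If allocation is simple, 40/40 is unlikely (8.9%), though missing it does little harm. If about half the subjects are sub-acute, a phase gap of 15 points or more arises in about 22-24% of trials; with a 0.10 m/s difference in recovery, a 15-point gap moves the contrast by about 0.3-0.4 of a standard error. The precision to be gained is about 6-10% of the variance of change. The phase share, the recovery difference and the SD are all assumed. Stratified blocks should not be expected to deliver exactly 40/40: they bring the arms close to it and nearly remove phase imbalance.

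**What to change.** In section 5.1, state the scheme: a computer-generated permuted-block list with varying block sizes, stratified by stroke phase only, using one pre-stated cut between sub-acute and chronic. Say who holds the list and how it is concealed. Describe 40 per group as a target that this list will approach to within about 2-3. Leave clinic out of the strata, since six strata would loosen control of the arm sizes.

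In section 8.3, prespecify stroke phase (or log days since stroke) and clinic as terms in the gait-speed model.

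The cost is slightly more list administration, a few degrees of freedom, and some predictability of the next assignment because treating therapists and subjects know the group. Varying the block sizes limits that predictability.
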